## 10.2 Triplet schedule

	Pre-Study	C1 Wk1	C1 Wk2	C1 Wk3	C1 Wk4	C1 Wk5	C1 Wk6	C2 Wk1	C2 Wk2	C2 Wk3	C2 Wk4	C2 Wk5	C2 Wk6	Off Treatment
Study drug		rhIL-15 + nivolumab + ipilimumaba												
Informed consent	X													
Demographics	X													
Medical history	X													
HIV/hepatitis screening b	X													
Concurrent meds	X	X-----X												
Physical exam c	X	X l	X	X	X	X	X	X	X	X	X	X	X	X
Vital signs c	X	X l	X	X	X	X	X	X	X	X	X	X	X	X
Height	X													
Weight	X	X l			X	X	X	X	X	X	X	X	X	X
Performance status c	X	X l	X	X	X	X	X	X	X	X	X	X	X	X
CBC w/diff, plts c	X	X l	X	X	X	X	X	X	X	X	X	X	X	X
Serum chemistry c, d	X	X l	X	X	X	X	X	X	X	X	X	X	X	X
Fasting lipid profile f	X	X l					X							X
Urinalysis c, e	X	X l	X	X	X	X	X	X	X	X	X	X	X	X
CPK/troponin I f	X	X l					X							
EKG, ECHO g	X													
Adverse event evaluation		X-----X												
Tumor measurements	X	Tumor measurements are repeated every cycle (every 6 weeks) ± 1 week during cycles 1-4 and every 2 cycles (every 12 weeks) ± 1 week thereafter. Documentation must be provided for patients removed from study for progressive disease. k												
B-HCG h	X													

Biopsy i	X						X							
Blood for PD k	X	X	X		X		X	X		X			X	
Blood for genomics m														

a. Each treatment cycle is 42 days long (cycle start +7 days/ drug administration + 3 days due to toxicities or +/- 3 days for scheduling conflicts; minimum of 12 days between nivolumab doses). rhIL-15 given SC days 1-8 and 22-29 (first 4 cycles only) + nivolumab given IV on days 8, 22, and 36 + ipilimumab given IV on day 8. Cycles 5 and onwards will not include rhIL-15; patients will receive nivolumab on days 1, 15, and 29 and ipilimumab on day 1. A 1-week Transition Period will be required between Cycle 4 and Cycle 5 to ensure a 2-week period between nivolumab doses. See Triplet Schema.
 
b. Hepatitis B Surface Antigen, Hepatitis B Surface Antibody, Hepatitis B Core Antibody, Hepatitis C Core Antibody, and HIV 1/2 serologies as part of screening evaluation.
 
c. Performed pre-study, weekly during cycles 1 and 2, and within 7 days prior to the start of every subsequent cycle.
 
d. ACTH, Albumin, alkaline phosphatase, amylase, total bilirubin, bicarbonate, BUN, calcium, chloride, cortisol (a.m.), creatinine, glucose, LDH, lipase, phosphorus, potassium, total protein, SGOT [AST], SGPT [ALT], sodium, TSH. (For patients on replacement hydrocortisone for adrenal insufficiency, ACTH and cortisol can be omitted from the laboratory evaluation.)
 
e. Protein/creatinine ratio.
 
f. Baseline and within 7 days of the start of every cycle.
 
g. Baseline and as clinically indicated.
 
h. Serum or urine pregnancy test (women of childbearing potential) as part of screening evaluation, and before the start of each cycle.
 
i. Research biopsies (optional during escalation phase; mandatory during expansion phase). At baseline and C1D42 (up to 3 days prior) as described in Section 9.1. Patients that respond to treatment and have baseline biopsy samples available may be asked to undergo an additional optional biopsy.
 
j. Blood for PD (mandatory). At baseline; on days 1-3, day 8 (before ipi + nivo), day 15 ± 2 days day 22 ± 2 days, and day 36 ± 2 days during Cycles 1-4; on days 1, 15, and 29 during Cycle 5 and onwards, as described in Section 9.3.
 
k. Patients positive for tumor markers (PSA, CEA, CA125) will have their serum levels remeasured at the time of radiographic restaging, as described in Section 5.
 
l. Values from eligibility screening evaluations may be used as baseline values if test was performed within 8 days of start of protocol therapy.
 
m. Blood for germline sequencing will be collected as needed from patients who respond to treatment and agree to undergo an additional biopsy for genomic analysis.
														

## 11. MEASUREMENT OF EFFECT

### ANTITUMOR EFFECT – SOLID TUMORS

Response and progression will be evaluated in this study using the international criteria proposed by the revised Response Evaluation Criteria in Solid Tumors (RECIST) guideline (version 1.1) [82]. Changes in the largest diameter (unidimensional measurement) of the tumor lesions and the shortest diameter in the case of malignant lymph nodes are used in the RECIST criteria.

Overall response will also be explored using iRECIST (see [Section 11.2](#)). Increasing clinical experience indicates that traditional response criteria such as RECIST may not be sufficient to fully characterize activity in the new era of target therapies and/or biologics. In studies with therapeutic antibodies, complete response, partial response, or stable disease has been shown to occur after an increase in tumor burden, characterized by progressive disease by traditional response criteria. Therefore, conventional response criteria may not adequately assess the activity of immunotherapeutic agents because progressive disease (by initial radiographic evaluation) does not necessarily reflect therapeutic failure. Long-term effect on the target disease must also be captured. The immune RECIST (iRECIST) criteria, by incorporating specific response patterns that have been observed with immunotherapeutic agents, have been developed to address these issues and provide standardized response criteria for use with immunotherapy [79].

#### 11.1 RECIST v1.1 Criteria for Assessment of Response and Progression

##### Definitions

Evaluable for toxicity. All patients will be evaluable for toxicity from the time of their first treatment.

Evaluable for objective response. All patients who met the eligibility criteria (with the possible exception of those who received no study medication) should be included in the main analysis of response to treatment. These patients will have their response classified according to the definitions stated below.

Evaluable Non-Target Disease Response. Patients who have lesions present at baseline that are evaluable but do not meet the definitions of measurable disease will be considered evaluable for non-target disease. The response assessment is based on the presence, absence, or unequivocal progression of the lesions.

##### Disease Parameters

Measurable disease. Measurable lesions are defined as those that can be accurately

measured in at least one dimension (longest diameter to be recorded) as  $\geq 20$  mm ( $\geq 2$  cm) by chest x-ray or as  $\geq 10$  mm ( $\geq 1$  cm) with CT scan, MRI, or calipers by clinical exam. All tumor measurements must be recorded in millimeters (or decimal fractions of centimeters).

Malignant lymph nodes. To be considered pathologically enlarged and measurable, a lymph node must be  $\geq 15$  mm ( $\geq 1.5$  cm) in short axis when assessed by CT scan (CT scan slice thickness recommended to be no greater than 5 mm [0.5 cm]). At baseline and in follow-up, only the short axis will be measured and followed.

Non-measurable disease. All other lesions (or sites of disease), including small lesions (longest diameter  $< 10$  mm [ $< 1$  cm] or pathological lymph nodes with  $\geq 10$  to  $< 15$  mm [ $\geq 1$  to  $< 1.5$  cm] short axis), are considered non-measurable disease. Bone lesions, leptomeningeal disease, ascites, pleural/pericardial effusions, lymphangitis cutis/pulmonitis, inflammatory breast disease, and abdominal masses (not followed by CT or MRI), are considered as non-measurable.

Note: Cystic lesions that meet the criteria for radiographically defined simple cysts should not be considered as malignant lesions (neither measurable nor non-measurable) since they are, by definition, simple cysts.

‘Cystic lesions’ thought to represent cystic metastases can be considered as measurable lesions, if they meet the definition of measurability described above. However, if non-cystic lesions are present in the same patient, these are preferred for selection as target lesions.

Target lesions. All measurable lesions up to a maximum of 2 lesions per organ and 5 lesions in total, representative of all involved organs, should be identified as **target lesions** and recorded and measured at baseline. Target lesions should be selected on the basis of their size (lesions with the longest diameter), be representative of all involved organs, but in addition should be those that lend themselves to reproducible repeated measurements. It may be the case that, on occasion, the largest lesion does not lend itself to reproducible measurement in which circumstance the next largest lesion which can be measured reproducibly should be selected. A sum of the diameters (longest for non-nodal lesions, short axis for nodal lesions) for all target lesions will be calculated and reported as the baseline sum diameters. If lymph nodes are to be included in the sum, then only the short axis is added into the sum. The baseline sum diameters will be used as reference to further characterize any objective tumor regression in the measurable dimension of the disease.

Non-target lesions. All other lesions (or sites of disease) including any measurable lesions over and above the 5 target lesions should be identified as **non-target lesions** and should also be recorded at baseline. Measurements of these lesions are not required, but the presence, absence, or in rare cases unequivocal progression of each should be noted throughout follow-up.

### Methods for Evaluation of Measurable Disease

All measurements should be taken and recorded in metric notation using a ruler or calipers. All baseline evaluations should be performed as closely as possible to the beginning of treatment and never more than 4 weeks before the beginning of the treatment.

The same method of assessment and the same technique should be used to characterize each identified and reported lesion at baseline and during follow-up. Imaging-based evaluation is preferred to evaluation by clinical examination unless the lesion(s) being followed cannot be imaged but are assessable by clinical exam.

Clinical lesions: Clinical lesions will only be considered measurable when they are superficial (e.g., skin nodules and palpable lymph nodes) and  $\geq 10$  mm ( $\geq 1$  cm) diameter as assessed using calipers (e.g., skin nodules). In the case of skin lesions, documentation by color photography, including a ruler to estimate the size of the lesion, is recommended.

Chest x-ray: Lesions on chest x-ray are acceptable as measurable lesions when they are clearly defined and surrounded by aerated lung. However, CT is preferable.

Conventional CT and MRI: This guideline has defined measurability of lesions on CT scan based on the assumption that CT slice thickness is 5 mm (0.5 cm) or less. If CT scans have slice thickness greater than 5 mm (0.5 cm), the minimum size for a measurable lesion should be twice the slice thickness. MRI is also acceptable in certain situations (e.g. for body scans).

Use of MRI remains a complex issue. MRI has excellent contrast, spatial, and temporal resolution; however, there are many image acquisition variables involved in MRI, which greatly impact image quality, lesion conspicuity, and measurement. Furthermore, the availability of MRI is variable globally. As with CT, if an MRI is performed, the technical specifications of the scanning sequences used should be optimized for the evaluation of the type and site of disease. Furthermore, as with CT, the modality used at follow-up should be the same as was used at baseline and the lesions should be measured/assessed on the same pulse sequence. It is beyond the scope of the RECIST guidelines to prescribe specific MRI pulse sequence parameters for all scanners, body parts, and diseases. Ideally, the same type of scanner should be used and the image acquisition protocol should be followed as closely as possible to prior scans. Body scans should be performed with breath-hold scanning techniques, if possible.

PET-CT: At present, the low dose or attenuation correction CT portion of a combined PET-CT is not always of optimal diagnostic CT quality for use with RECIST measurements. However, if the site can document that the CT performed as part of a PET-CT is of identical diagnostic quality to a diagnostic CT (with IV and oral contrast), then the CT portion of the PET-CT can be used for RECIST measurements and can be used interchangeably with conventional CT in accurately measuring cancer lesions over time. Note, however, that the PET portion of the CT introduces additional data which may bias an investigator if it is not routinely or serially performed.

Ultrasound: Ultrasound is not useful in assessment of lesion size and should not be used as a method of measurement. Ultrasound examinations cannot be reproduced in their entirety for independent review at a later date and, because they are operator dependent, it cannot be guaranteed that the same technique and measurements will be taken from one assessment to the next. If new lesions are identified by ultrasound in the course of the study, confirmation by CT or MRI is advised. If there is concern about radiation exposure at CT, MRI may be used instead of CT in selected instances.

Endoscopy, Laparoscopy: The utilization of these techniques for objective tumor evaluation is not advised. However, such techniques may be useful to confirm complete pathological response when biopsies are obtained or to determine relapse in trials where recurrence following complete response (CR) or surgical resection is an endpoint.

Tumor markers: Tumor markers alone cannot be used to assess response. If markers are initially above the upper normal limit, they must normalize for a patient to be considered in complete clinical response. Specific guidelines for both CA-125 response (in recurrent ovarian cancer) and PSA response (in recurrent prostate cancer) have been published [*JNCI* 96:487-488, 2004; *J Clin Oncol* 17, 3461-3467, 1999; *J Clin Oncol* 26:1148-1159, 2008]. In addition, the Gynecologic Cancer Intergroup has developed CA-125 progression criteria which are to be integrated with objective tumor assessment for use in first-line trials in ovarian cancer [*JNCI* 92:1534-1535, 2000].

Cytology, Histology: These techniques can be used to differentiate between partial responses (PR) and complete responses (CR) in rare cases (e.g., residual lesions in tumor types, such as germ cell tumors, where known residual benign tumors can remain).

The cytological confirmation of the neoplastic origin of any effusion that appears or worsens during treatment when the measurable tumor has met criteria for response or stable disease is mandatory to differentiate between response or stable disease (an effusion may be a side effect of the treatment) and progressive disease.

FDG-PET While FDG-PET response assessments need additional study, it is sometimes reasonable to incorporate the use of FDG-PET scanning to complement CT scanning in assessment of progression (particularly possible 'new' disease). New lesions on the basis of FDG-PET imaging can be identified according to the following algorithm:

- a. Negative FDG-PET at baseline, with a positive FDG-PET at follow-up is a sign of PD based on a new lesion.
- b. No FDG-PET at baseline and a positive FDG-PET at follow-up: If the positive FDG-PET at follow-up corresponds to a new site of disease confirmed by CT, this is PD. If the positive FDG-PET at follow-up is not confirmed as a new site of disease on CT, additional follow-up CT scans are needed to determine if there is truly progression occurring at that site (if so, the date of PD will be the date of the initial abnormal FDG-PET scan). If the positive FDG-PET at follow-up corresponds to a pre-existing site of disease on CT that is not progressing on the basis of the anatomic images, this is not PD.
- c. FDG-PET may be used to upgrade a response to a CR in a manner similar to a biopsy

in cases where a residual radiographic abnormality is thought to represent fibrosis or scarring. The use of FDG-PET in this circumstance should be prospectively described in the protocol and supported by disease-specific medical literature for the indication. However, it must be acknowledged that both approaches may lead to false positive CR due to limitations of FDG-PET and biopsy resolution/sensitivity.

Note: A ‘positive’ FDG-PET scan lesion means one which is FDG avid with an uptake greater than twice that of the surrounding tissue on the attenuation corrected image.

### Response Criteria

#### **11.1.1** Evaluation of Target Lesions

Complete Response (CR): Disappearance of all target lesions. Any pathological lymph nodes (whether target or non-target) must have reduction in short axis to <10 mm (<1 cm).

Partial Response (PR): At least a 30% decrease in the sum of the diameters of target lesions, taking as reference the baseline sum diameters.

Progressive Disease (PD): At least a 20% increase in the sum of the diameters of target lesions, taking as reference the smallest sum on study (this includes the baseline sum if that is the smallest on study). In addition to the relative increase of 20%, the sum must also demonstrate an absolute increase of at least 5 mm (0.5 cm). (Note: the appearance of one or more new lesions is also considered progressions). In exceptional circumstances, unequivocal progression of non-target disease may be accepted as evidence of disease progression, where the overall tumour burden has increased sufficiently to merit discontinuation of treatment or where the tumour burden appears to have increased by at least 73% in volume. Modest increases in the size of one or more non-target lesions are NOT considered unequivocal progression. If the evidence of PD is equivocal (target or non-target), treatment may continue until the next assessment, but if confirmed, the earlier date must be used.

Patients that are clinically well may continue on therapy following RECIST progression with new lesions or increase in target lesions if the increase in disease burden does not meet the definition of PD by immune response criteria [79]. In this situation, patients do not have unequivocal progression until immune response criteria are met (see [Section 11.2](#)).

Stable Disease (SD): Neither sufficient shrinkage to qualify for PR nor sufficient increase to qualify for PD, taking as reference the smallest sum diameters while on study.

#### **11.1.2** Evaluation of Non-Target Lesions

Complete Response (CR): Disappearance of all non-target lesions and normalization of tumor marker level. All lymph nodes must be non-pathological in size (<10 mm [<1 cm] short axis).

Note: If tumor markers are initially above the upper normal limit, they must normalize for a patient to be considered in complete clinical response.

**Non-CR/Non-PD:** Persistence of one or more non-target lesion(s) and/or maintenance of tumor marker level above the normal limits.

**Progressive Disease (PD):** Appearance of one or more new lesions and/or *unequivocal progression* of existing non-target lesions. *Unequivocal progression* should not normally trump target lesion status. It must be representative of overall disease status change, not a single lesion increase.

Although a clear progression of “non-target” lesions only is exceptional, the opinion of the treating physician should prevail in such circumstances, and the progression status should be confirmed at a later time by the review panel (or Principal Investigator).

### 11.1.3 Evaluation of Best Overall Response

The best overall response is the best response recorded from the start of the treatment until disease progression/recurrence (taking as reference for progressive disease the smallest measurements recorded since the treatment started). The patient's best response assignment will depend on the achievement of both measurement and confirmation criteria.

#### For Patients with Measurable Disease (*i.e.*, Target Disease)

Target Lesions	Non-Target Lesions	New Lesions	Overall Response	Best Overall Response when Confirmation is Required*
CR	CR	No	CR	$\geq 4$ wks. Confirmation**
CR	Non-CR/Non-PD	No	PR	
CR	Not evaluated	No	PR	
PR	Non-CR/Non-PD/not evaluated	No	PR	
SD	Non-CR/Non-PD/not evaluated	No	SD	Documented at least once $\geq 4$ wks. from baseline**
PD	Any	Yes or No	PD	no prior SD, PR or CR
Any	PD***	Yes or No	PD	
Any	Any	Yes	PD	

\* See RECIST 1.1 manuscript for further details on what is evidence of a new lesion.  
\*\* Only for non-randomized trials with response as primary endpoint.  
\*\*\* In exceptional circumstances, unequivocal progression in non-target lesions may be accepted as disease progression.

Note: Patients with a global deterioration of health status requiring discontinuation of treatment without objective evidence of disease progression at that time should be reported as “*symptomatic deterioration*.” Every effort should be made to document the objective progression even after discontinuation of treatment.

### For Patients with Non-Measurable Disease (i.e., Non-Target Disease)

Non-Target Lesions	New Lesions	Overall Response
CR	No	CR
Non-CR/non-PD	No	Non-CR/non-PD*
Not all evaluated	No	not evaluated
Unequivocal PD	Yes or No	PD
Any	Yes	PD

\* ‘Non-CR/non-PD’ is preferred over ‘stable disease’ for non-target disease since SD is increasingly used as an endpoint for assessment of efficacy in some trials so to assign this category when no lesions can be measured is not advised

## 11.2 iRECIST Response Assessment

Overall response will also be explored using iRECIST [79]. Immunotherapeutics may result in infiltration of immune cells leading to transient increase in the size in malignant lesions, resulting in previously undetectable lesions becoming detectable. The criteria are identical to those of RECIST 1.1 in many respects but have been adapted to account for instances where an increase in tumour burden, or the appearance of new lesions, does not reflect true tumour progression.

Key differences between RECIST 1.1 and iRECIST are described below. All responses defined using iRECIST criteria are designated with a prefix. iRECIST time-point and best overall responses will be recorded separately.

### Confirming Progression

Unlike RECIST 1.1, iRECIST requires the confirmation of progression and uses the terms iUPD (unconfirmed progression) and iCPD (confirmed progression). Confirmatory scans should be performed at least 4 weeks, but no longer than 8 weeks after iUPD.

iCPD is confirmed if further progression, compared to the last assessment, is seen as evidenced by one or more of the following:

- Continued progression where RECIST 1.1 definitions of progression had been met (from nadir) in target, non-target disease or new lesions (from uPD):
  - Progression in target disease worsens with an increase of at least 5 mm in the absolute value of the sum;
  - Continued unequivocal progression in non-target disease with an increase in tumor burden;
  - Increase in size of previously identified new lesion(s) (an increase of at least 5 mm in the absolute value of the sum of those considered to be target new lesions);
- RECIST 1.1 criteria are met where progression was not previously identified, including

the appearance of additional new lesions.

If iUPD is not confirmed at the next assessment, then the appropriate response will be assigned (iUPD is the criteria are still met, but no worsening, or iSD, iPR or iCR if those criteria are met compared to baseline). As can be seen in the below table, the prior documentation of iUPD does not preclude assigning iCR, iPR, or iSD in subsequent time-point assessments or as best overall response (BOR) providing that iCPD is not documented.

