### Time-point (TP) iResponse

Target Lesions*	Non-Target Lesions*	New Lesions*	Time Point Response	
			No prior iUPD**	Prior iUPD**
CR / iCR	CR	No	CR	iCR
CR/iCR	Non-CR/Non-PD Non-iCR/Non-iUPD	No	PR	iPR
PR/iPR	Non-CR/Non-PD Non-iCR/Non-iUPD	No	PR	iPR
SD/iSD	Non-CR/Non-PD Non-iCR/Non-iUPD	No	SD	iSD
iUPD with no change OR decrease from last TP	iUPD with no change OR decrease from last TP	Yes	NA	The appearance NLs confirms PD if Additional NLs or iUPD in last TP based on NLs and increase in size ( $\geq 5$ mm for NLT or any increase for NLNT) If no change in NLs from last TP, remains iUPD
PD	Non-CR/Non-PD Non-iCR/Non-iUPD	No	iUPD	Remains iUPD unless iCPD confirmed based on further increase in sum of at least 5 mm, otherwise remains iUPD

PD	PD	No	iUPD	iCPD if further increase in previously identified*** T lesion iUPD $\geq$ 5 mm and / or NT lesion iUPD
PD	PD	Yes	iUPD	iCPD if further increase in previously identified T lesion iUPD $\geq$ 5 mm and / or NT lesion iUPD and / or size or number of new lesion
Non-iUPD	Non-iUPD	Yes	iUPD	iCPD if increase in size of previously identified new lesions or increased number of new lesion

\* Using RECIST 1.1 principles. If no pseudoprogression occurs, RECIST 1.1 and iRECIST categories for CR, PR and SD would be the same.  
 \*\* In any category.  
 \*\*\* Previously identified in assessment immediately prior to this time-point (TP)  
 NA = not applicable.

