### iRECIST Best Overall Response (iBOR)

All patients will have their iBOR from the start of study treatment until the end of treatment classified as outlined below.

TPR1	TPR2	TPR3	TPR4	TPR5	iBOR
CR	CR, PR, iUPD, NE	CR/iCR, PR/iPR, iUPD, iCPD, NE	iUPD	iCPD	iCR
iUPD	PR, SD, NE	CR	CR, PR, SD, iUPD, NE	CR, PR, SD, iUPD, iCPD, NE	iCR
iUPD	PR	PR, SD, iUPD, NE	PR, SD, iUPD, NE, cPD	PR, SD, iUPD, NE, iCPD	iPR
iUPD	SD, NE	PR	PR, SD, iUPD, NE	PR, SD, iUPD, iCPD, NE	iPR
iUPD	SD	SD, iUPD, NE	SD, iUPD, iCPD, NE	SD, iUPD, iCPD, NE	iSD
iUPD	iUPD	Anything	Anything	Anything	iCPD
iUPD	iUPD	iCPD	Anything	Anything	iCPD
iUPD	NE	NE	NE	NE	iUPD

1. Table assumes a randomized study where confirmation of CR or PR is not required.
2. NE = not evaluable that cycle.
3. Designation "I" for BOR can be used to indicate prior uPD to aid in data interpretation.
4. For patients with non-target disease only at baseline, only CR or non-CR/non-PD can be assigned at each TPR but is not shown in the table for ease of presentation.

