### **13.2 Sample Size/Accrual Rate**

With an anticipated accrual of 3-4 patients per month, it is expected that accrual can be completed in 16 months. The minimum number of patients enrolled in this trial will be 15 and the maximum number of patients enrolled will be 45, including an expansion cohort of 15 patients that will be treated at the MTD or the maximum administered dose. To allow for unevaluable patients, the accrual ceiling has been set at 50 patients.

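### Row 6 of the iRECIST best-overall-response table scores two unconfirmed progressions as confirmed progression whatever follows, against the text of Section 11.2

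*Combined protocol and SAP*

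**What the plan says.** Section 11.2, Confirming Progression, makes iCPD depend on further progression relative to the last assessment. If iUPD is not confirmed at the next scan, the patient is assigned "iUPD is the criteria are still met, but no worsening, or iSD, iPR or iCR if those criteria are met compared to baseline" (the first *is* evidently stands for *if*). The section adds that "the prior documentation of iUPD does not preclude assigning iCR, iPR, or iSD in subsequent time-point assessments or as best overall response", on condition that iCPD has not been documented.

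The Time-point (TP) iResponse table agrees. For target-lesion progression in a patient with prior iUPD it reads "Remains iUPD unless iCPD confirmed based on further increase in sum of at least 5 mm, otherwise remains iUPD".

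The iBOR table then classifies every patient from up to five time-point responses (TPR1 to TPR5). Its sixth row reads "iUPD iUPD Anything Anything Anything iCPD", and its fourth reads "iUPD SD, NE PR PR, SD, iUPD, NE PR, SD, iUPD, iCPD, NE iPR". Row 7 is iUPD, iUPD, iCPD, then anything, also giving iCPD. Note 1 says "Table assumes a randomized study where confirmation of CR or PR is not required".

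**The concern.** Row 6 turns two unconfirmed progressions into confirmed progression without any scan having met the definition of confirmation, and nothing seen later can change the result. iRECIST is used here because apparent early progression may be followed by response (Sections 11 and 11.2), and the iRECIST response rate is part of exploratory objective 1.2.1. Applied literally, row 6 removes late responders from the numerator, so its error in the response rate can only be downward. One analyst following the text and another following the table could report different rates from the same scans.

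The sequence can arise. Section 5.4 lets clinically well patients continue past RECIST progression until the immune criteria are met, and scans are six-weekly in cycles 1 to 4. Two unconfirmed progressions at about weeks 6 and 12 could therefore be followed by a response at week 18 or 24.

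**Working it through.** The plan gives no figure to reproduce here; the check is logical.

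**Inputs.** iBOR rows 2 to 7, the Confirming Progression text and the time-point table (Section 11.2); expansion cohort of 15 (Section 5.1.2.2); 3 to 6 patients at each of three triplet dose levels (Section 5.1.2); "the maximum number of patients enrolled will be 45" (Section 13.2).

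**Step 1: specific sequences.** The text rule is the best CR, PR or SD recorded before any iCPD; failing that, iCPD if documented; otherwise iUPD. Counting a response that precedes a later iCPD follows rows 2 to 5, which allow iCPD at later assessments.

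| TPR1 to TPR5 | Row 6 | Text rule |
|---|---|---|
| iUPD, iUPD, CR, CR, CR | iCPD | iCR |
| iUPD, iUPD, PR, PR, PR | iCPD | iPR |
| iUPD, iUPD, SD, SD, SD | iCPD | iSD |
| iUPD at all five | iCPD | iUPD |
| iUPD, iUPD, iCPD, iCPD, iCPD | iCPD | iCPD |

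The first four contain no iCPD, so the condition attached to the text rule is met and does not rescue row 6.

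**Step 2: all continuations without iCPD.** With TPR3 to TPR5 each one of CR, PR, SD, iUPD or not evaluable (NE), there are 5³ = 125 sequences after iUPD, iUPD. Under the text:

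- iCR (at least one CR): 5³ − 4³ = 125 − 64 = 61
- iPR (no CR, at least one PR): 4³ − 3³ = 64 − 27 = 37
- iSD (no CR or PR, at least one SD): 3³ − 2³ = 27 − 8 = 19
- iUPD (only iUPD or NE): 2³ = 8
- iCPD: 0

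The total is 61 + 37 + 19 + 8 = 125. Row 6 assigns iCPD to all 125. Response status changes in 61 + 37 = 98 of them; the other 27 are non-responses either way.

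Allowing iCPD as well gives 6³ = 216 continuations. The text rule gives iCPD for 52 and something else for 164 (76 iCR, 50 iPR, 30 iSD, 8 iUPD). Row 6 gives iCPD for all 216.

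**Step 3: the table against itself.**

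- Row 4 scores iUPD, NE, PR as iPR, while row 6 scores iUPD, iUPD, PR as iCPD. A missed second scan scores better than an unchanged one.
- All 6² = 36 sequences of row 7 lie inside row 6, so row 7 does nothing if row 6 stands.
- No row covers iUPD followed directly by iCPD, the simplest confirmed progression.

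A single wrong entry, iUPD for iCPD at TPR2 of row 6, would explain the last two points.

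**Step 4: effect on the response rate.** The number of affected patients is not given; 1 to 3 is an assumption. The loss is k/n:

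| Denominator | k = 1 | k = 3 |
|---|---|---|
| Expansion cohort, 15 | 1/15 = 6.7 points | 3/15 = 20.0 points |
| Maximum triplet slots, 3 × 6 + 15 = 33 | 1/33 = 3.0 points | 3/33 = 9.1 points |
| Planned maximum, 45 | 1/45 = 2.2 points | 3/45 = 6.7 points |

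**The case against.** The strongest objection is that everything turns on one letter in one cell of a table read from PDF, and row 3 of the same table already has an irregular label (cPD where other rows have iCPD). A reading error cannot be ruled out, so the source page must be checked first. If it shows iCPD in that cell, the conflict in row 6 disappears.

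The text and the time-point table are also clear, so bias arises only if someone applies row 6 literally. That is true, but the protocol says all patients are classified by this table, and none of its four notes gives the text precedence.

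The table is not exhaustive either: no row starts with SD or PR. This weakens the argument from the missing iUPD-then-iCPD row and supports a general default note. It does not excuse a row that is present and wrong.

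On size, the counts are patterns, the 1 to 3 patients have no support in the documents, and the triplet-only denominator of 33 fits objective 1.2.1 better than 45, because the doublets are described as safety-only. All of this stands. The smaller denominator makes each misclassification larger, not smaller.

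Finally, the endpoint is exploratory and reported with caveats. That limits the importance of the point but not its correctness.

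**Conclusion.** The concern holds. As printed, row 6 contradicts the confirmation rule in Section 11.2, the time-point table and row 4 of its own table. It misclassifies all 125 continuations in which progression is never confirmed, and 98 of those would be responses under the text. The cost per affected responder is 6.7 points at n = 15, 3.0 at n = 33 and 2.2 at n = 45; how many patients would be affected is unknown. The conclusion assumes that the printed row matches the source page and that the table would be applied as written. DLT, MTD, dose escalation and RECIST 1.1 response do not depend on it, and no decision rule uses the iRECIST rate. It should be corrected before best overall response is derived.

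The reference to a randomized study in note 1 is a minor slip, since this trial is not randomized. Its working part, that CR and PR need no confirmation, agrees with the footnote in Section 11.1.3 that limits confirmation: "Only for non-randomized trials with response as primary endpoint". Response is exploratory here.

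**What to change.** 1. Check the source page. If it reads as printed here, change TPR2 of row 6 from iUPD to iCPD. This also supplies the missing iUPD-then-iCPD row.
2. Add one row, because the cell change alone leaves none of the 125 sequences with a matching row. For iUPD, iUPD without iCPD at TPR3, iBOR is the best iCR, iPR or iSD recorded before any iCPD; if there is none, iCPD when later documented, otherwise iUPD.
3. Add a note that any sequence not listed follows the Section 11.2 text.
4. In note 1, drop the assumption of a randomized study and keep the statement that confirmation of CR or PR is not required. The opening paragraph of Section 11.1.3 mentions confirmation criteria in general terms and should be made consistent.

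The cost is one table cell, one row and two short notes, with no new data, scans or patients.

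Separately, the 4 to 8 week window for confirmatory scans in Section 11.2 and the 12-weekly scans from cycle 5 should be reconciled. No rule is proposed here.
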